ii) Clinical Significance	page 27
III) Research Design and Methods	page 29
IV) Protection of Human Subjects	page 33
V) Adequacy of Protection against Risks	page 35
VI) Subject Safety and Minimizing Risks	page 42
VII) Consultants	page 43
VIII) Facilities Available	page 44
IX) Appendices	page 45
X) References	page 71

I) SPECIFIC AIMS

i) Aim 1

The primary outcome is to assess the safety and toxicity profile of the combination of famotidine and oral n-acetyl cysteine in adult outpatients with newly diagnosed SARS-CoV-2 infection.

ii) Hypothesis 1

We hypothesize that the combination of famotidine and n-acetyl cysteine are a safe combination of therapies in adult outpatients with newly diagnosed SARS-CoV-2 infection.

iii) Aim 2

The secondary outcome is to assess whether certain markers (e.g., IL-1 β , IL-2, IL-6, Tryptase, Glutathione, F2-Isoprostane/Creatinine, N-methylhistamine, CAP-SYM 18, IPSS and CURB-65) are predictive of outcomes and/or treatment response.

iv) Hypothesis 2

We hypothesize that treatment with the combination of n-acetyl cysteine and famotidine in addition to the potential for reducing the primary endpoint of risk of hospitalization may also affect specific markers of infection which may prove useful surrogates for predicting the severity of the infection.

II) BACKGROUND AND SIGNIFICANCE

i) Background

N-Acetyl Cysteine (NAC) is a prodrug to L-cysteine which is a precursor to the biologic antioxidant glutathione. Administration is FDA approved for acetaminophen poisoning for which it is nearly 100% effective if given within 8 hours¹ and works through replenishing glutathione stores.²

Famotidine is a histamine-2 (H₂) receptor antagonist. Administration is approved in adult and pediatric patients 40 kg and above for the treatment of active duodenal ulcer, active gastric ulcer, symptomatic non-erosive gastroesophageal reflux disease (GERD), and erosive esophagitis due to GERD if diagnosed by biopsy. Administration is also approved in adults for the treatment of pathological hypersecretory conditions (e.g., Zollinger-Ellison Syndrome, multiple endocrine neoplasias) and for the reduction of the risk of duodenal ulcer recurrence.

There have been no studies on the use of the combination of FAM and NAC in the treatment of outpatients who test positive for SARS-CoV-2 infection.

a) Biochemical rationale

1. **Angiotensin Converting Enzyme 2 (ACE2) is SARS-CoV-2 Virus Binding Site**

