ischemia/reperfusion injury by disturbing mitochondrial and endothelial function.¹⁶¹ In fact famotidine was demonstrated to abolish the effect of H2R agonists on rat cardiomyocytes to induce apoptosis, increase mitochondrial permeability and increase caspase 3 expression.

A 2016 study demonstrates that macrolides induced ROS and increased the mitochondrial membrane permeability in rat cardiac myocytes.¹⁶² The authors make the case based on these results and a body of literature about the relationship between MMP and QT interval prolongation that, this may be the mechanism in which macrolides can lead to QT interval prolongation. What is most fascinating about this study is that the authors demonstrated that NAC reversed the effect on the mitochondria from the macrolides.

In addition to this data in macrolides, there is also data in mice with a knockout NOS1Ap (neuronal nitric oxide synthase-1 adaptor protein), which is associated with QT interval prolongation and sudden death, in which oxidative stress was induced by an injection of doxorubicin. The knockout mice compared to WT mice not surprisingly had significant prolongation of QT interval, higher rates of ventricular arrhythmias, higher rates of death, and higher measured levels of H₂O₂. Administration of NAC to the knockout mice, significantly reduced mortality by doxorubicin injection, accompanied by prevention of QT interval prolongation.¹⁶⁰

There is also data in rats which were irradiated while heart monitoring was performed. The rats were found to have cardiac injury as observed on the EKG along with significant increases in cytokine levels and oxidative stress. Pretreatment with NAC ameliorated the cardiac injury induced by irradiation.¹⁶³

Thus, there are at least two potential mechanisms by which NAC and FAM may independently reduce a risk of QT interval prolongation that a SARS-CoV-2 infection may precipitate by dramatically increasing the level of IL-6.

In addition to the protection that NAC may provide from IL-6 and perhaps more importantly, NAC has been demonstrated to significantly reduce IL-6 levels in viral infections. NAC's ability to reduce IL-6 levels has been demonstrated in the H5N1 influenza A virus,⁷² H9N2 swine flu virus,¹⁴⁰ RSV,⁷⁰ and HIV.¹⁶⁴

14. Depletion of LC3-I is rate limiting in Coronavirus infection and NAC's demonstrated ability to dramatically increase LC3-II to LC3-I ratio

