Given the existing biochemical data to suggest FAM inhibits suppression of intraepithelial lymphocytes by histamine and Mast Cell release of histamine; the correlation of severity of tissue fibrosis and thrombosis with ACE2 depletion; the ability of NAC to reduce oxidative stress, which appears related to severity of the SARS-CoV-2 infection; the ability of NAC to prevent tissue fibrosis, thrombosis and reduce viral replication; the favorable side effect profiles of FAM and NAC; the wide prevalence of SARS-CoV-2 infection and its substantial mortality rate; and, the lack of vaccine or proven therapies for non-hospitalized patients who have tested positive for a SARS-CoV-2 infection; a clinical trial of the safety and efficacy of the combination of NAC and FAM is justified. These medications are readily available and their combination does have the possibility of reducing the severity of infection and mortality for these patients (see figure 9).¹⁷⁰

[figure not shown]

Figure 9: A cartoon drawing¹⁷⁰ of the putative effect of FAM to reduce inhibition of Intra-Epithelial Lymphocytes and of NAC to reduce severity of infection through reduction of oxidative stress and reduction of viral replication

III) RESEARCH DESIGN AND METHODS (including data analysis)

i) Study Design - Parallel Phase I/II Clinical Trial

The proposed parallel phase I/II design allows for simultaneously evaluating the safety and efficacy of combination dose levels and to select the optimal combination dose. The trial is started with an initial period of dose escalation, and then patients are randomly assigned to permissible dose levels. Bayesian posterior probabilities are used in the randomization to adaptively assign more patients to doses with higher efficacy levels. Combination doses with lower efficacy are temporarily closed and those with intolerable toxicity are eliminated. The trial is stopped if the posterior probability for safety, efficacy or futility crosses our pre-specified boundaries. This design has been shown in simulations to save sample size, to have better power and efficiently assigns more patients to doses with higher efficacy levels.¹⁷¹

Phase I Portion (Dose Escalation Phase)

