The doses to be tested for famotidine are 20 mg thrice daily, 40 mg thrice daily, 80 mg thrice daily and no famotidine. The doses to be tested for n-acetyl cysteine are 600 mg thrice daily, 1200 mg thrice daily and 1800 mg thrice daily. The dose combinations are labelled 1 through 12 and are zoned as illustrated in Figure 10. The first zone has the combination of the lowest dose of each drug. The second zone has the combination of the lowest dose of each drug with the middle dose of each drug. The dose escalation starts with the first zone and follows with the second zone and then each combination of doses in the zone next closest to the coordinate

[figure not shown]

Figure 10. Dose Combinations of N-Acetyl Cysteine and Famotidine

origin shown in figure 10. Combination doses in the same zone are tested simultaneously using block randomization to control the number of patients for each open dose. Some combinations doses may close, in which case blocked randomization is applied to the remaining open combination doses in the same zone. A modified “3+3” design¹⁷² will be used for the initial dose escalation.

To find acceptable dose levels any grade 3 or higher toxicity will be considered a dose-limiting toxicity (DLT). The modified “3+3” design proceeds as described below. Three patients receive dose level 1. Their responses determine the subsequent steps as described in the following decision rules.

- (1) If two patients (2/3) experience DLT, then we close dose level 1 and all larger doses to testing.
- (2) If no patient experiences DLT, then we designate dose level 1 as an admissible dose, and open doses in zone 2 for testing.
- (3) If only one of the first three patients (1/3) experiences DLT, then we assign three more patients to dose level 1. In this case, we assign up to six patients to this dose, and the following decision rules apply:
 - a. If only one of the six patients (1/6) experiences DLT, then we designate dose level 1 as an admissible dose, and open doses in zone 2 for testing.
 - b. If two of the six patients (2/6) experience DLT, then we designate dose level 1 as an admissible dose, and doses in zone 2 and higher are closed to testing.
 - c. If more than two of the six patients (>2/6) experience DLT, then we close dose level 1 to testing, and we also close doses in zone 2 and higher.

ii) Study Procedure

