The randomization process will be performed using the Randomization module within REDCAP®. This will be performed through use of the data entry form entitled, “COVID-19 Test Result and Drug Randomization Case Report Form.” If the subject has a Rapid Test Performed in the ED and a positive result is obtained prior to discharge, the Co-Investigator who enrolled the subject will be able to access this form and perform the randomization. Otherwise, the randomization will be performed by the PI. Due to the trial design as a Phase I trial, the number of subjects on any arm can vary from zero to six depending on any dose limiting toxicities that may occur. Also, a new zone in the trial will not be able to open until all subjects in the previous zone have completed the trial. Therefore, the randomization process will be dynamic which REDCap® is incapable of handling directly but is capable of handling indirectly in a two-step process as described below. Prior to the start up the trial, a randomization lookup table will be uploaded into REDCap®, which will be nothing more than an ordered table from one to one hundred. While this may seem trivial, it is utterly essential in order to harness the power of REDCap® for a dynamic randomization process. After an investigator has performed the randomization task in REDCap®, the randomization number will be returned from this table. The investigator will then be required to lookup manually the arm to which the subject has been randomized in a file called “Dynamic Randomization Lookup Table” which they will only find within the “File Repository” in REDCap®. An example of this file can be found in the Appendix below. This file will be created prior to the trial initiation by the Lead Statistical Investigator initially assuming three subjects for each trial arm. Anytime, a change is needed to the “Dynamic Randomization Lookup Table” due to a DLT, the PI will suspend the ability for anyone to enroll or randomize a subject through the “User Rights” feature of REDCap® which can be used to restrict access by role to data entry forms. Once a decision has been made about either expanding or closing a trial arm due to a

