Data will be exported from REDCap[®] using the Data Export Tool into a format that can be analyzed using R, JMP and/or SAS (SAS, Cary, NC). The User Rights in REDCap[®] will restrict the use of the REDCap[®] "Data Export Tool" to only the PI, Epidemiologist and the Statistical Co-Investigators. The rights will be further restricted within REDCap[®] such that only De-Identified data can be exported from Data Export Tool. Therefore, because no date or time fields can be extracted from REDCap[®] as described above, any Data Entry Form within REDCap[®] that collects a date has been created to include a hidden calculation field to calculate and store the number of days between such a date and either the enrollment date or the medication start date. Some dates are calculated based on the medication start date to make data collection easier on certain forms; however, the number of days between enrollment and medication start is also calculated and stored so that any number of elapsed days can easily be determined from either. After the data has been exported from REDCap into an aforementioned statistical package and descriptive statistics have been generated and analyzed by the Statistical Investigators. These results will be shared with the Epidemiologist and all Investigators so that appropriate conclusions can be reached and ultimately disseminated.

vi) Limitations of the Proposed Study Design

This is a phase I trial and may be limited by unmeasured confounders such as clinical practice patterns of the providers ordering initial SARS-CoV-2 testing. It also may be limited as subjects are being recruited directly from the ED and thus may be more symptomatic or have other unmeasured cofounders as compared to the general population who may become infected with SARS-CoV-2.

IV) PROTECTION OF HUMAN SUBJECTS

i) Risks To The Subjects

The main risks to Famotidine which have been occurred in greater than or equal to 1% of subjects in clinical trials are headache; dizziness and constipation.

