Assessment	Enrollment (within 24 hours of a SARS CoV-2 Test)	Weekly after Randomization Until Hospital Admission or Study Completion	Upon Study Completion (If SARS CoV-2 Positive)	If Hospitalized and Until Discharge
Informed Consent	X			
Urine Pregnancy Test (If appropriate)	X			
Blood Type and Rh	X			
(Serum) Cytokines (IL-1 β , IL-2, IL-6, IL-8, IL-10, IFN γ , TNF α and GM-CSF), Tryptase and Glutathione Level	X		X	X (once upon hospitalization)
(Urine) F2-Isoprostane/Creatinine Ratio, TMRSS2 Cytokines (IL-1 β , IL-2, IL-6, IL-8, IL-10, IFN γ , TNF α and GM-CSF) and N-methylhistamine	X	X	X	X (once upon hospitalization)
CURB-65 Score	X			
CAP-Sym 18	X			
IPSS (men only)	X			
Weekly Review of Daily Medication Logs and Daily Diary		X		
Weekly Assessment CRFs		X		
Completion Data CRF				
Hospital Tracking CRFs				
			X	X

Medication Log Form

Medication Log Form: Trial of FAM and NAC for SARS-CoV-2							
Subject Study Number: _____				Week #: _____			
Day of Week Trial Started: _____ (fill this in by hand under Day 1 below)							
Dose of Famotidine 20 mg tablets Assigned to Taken Thrice Daily: 0 1 2 3 (Research Staff to Circle)							
Number of N-Acetyl Cysteine Capsules Assigned to Take Thrice Daily: 1 2 3 (Research Staff to Circle)							
	Day 1	Day 2	Day 3	Day 4	Day 5	Day 6	Day 7
Day of Week							
Date (MM/DD)							
Famotidine (20 mg tablet)							
1 st Dose							
2 nd Dose							
3 rd Dose							
N-Acetyl Cysteine (600 mg capsule)							
1 st Dose							
2 nd Dose							
3 rd Dose							

Instructions for Research Staff:

1. Print a minimum of 4 Sheets and enter Subject Study Number on each. Write in week numbers 1 to 4 on each sheet.
2. Enter Day of Week Subject is to start taking medicine. This should be the same for each sheet.
3. Under Day 1 enter the day of the week that subject is to start taking medicine. Under each subsequent Day enter the next day of the week.
4. Circle the assigned number of Famotidine tablets to take thrice daily.
5. Circle the assigned number of N-Acetyl Cysteine capsules to take thrice daily.

Instructions for Research Subject:

1. You will be assigned to take one, two or three Famotidine tablets three times a day. Please enter the time of day for the correct day for each dose you take.
2. You will take the N-Acetyl Cysteine capsules thrice a day. You will be assigned to take one, two or three capsules each time. Please enter the time of day for the correct day for each dose you take.

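### Hypothesis 2 asks whether treatment affects markers, but only descriptive statistics are planned; an exploratory baseline-adjusted model pooled over the dose grid would use the same data better, within stated limits

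*Combined protocol and SAP*

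**What the plan says.** Under Specific Aims, Hypothesis 2 states that treatment "may also affect specific markers of infection which may prove useful surrogates for predicting the severity of the infection". The background, in the subsection on IL-6 and the QT interval, reports that "NAC has been demonstrated to significantly reduce IL-6 levels in viral infections", citing work on other viruses.

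The data to look at this are collected. Urine cytokines, F2-isoprostane/creatinine and N-methylhistamine are scheduled at enrollment and then "Weekly after Randomization Until Hospital Admission or Study Completion". Glutathione and tryptase are measured in blood only, at enrollment and once drug has stopped or the subject is hospitalized.

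On dose, the Phase I Portion says "The doses to be tested for n-acetyl cysteine are 600 mg thrice daily, 1200 mg thrice daily and 1800 mg thrice daily". These are crossed with four famotidine levels (none, 20, 40 and 80 mg) to give twelve combinations. The randomization table is built "initially assuming three subjects for each trial arm", and Study Procedure allows zero to six per arm.

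Data Analysis Methods (III.v) says only that "descriptive statistics have been generated and analyzed by the Statistical Investigators". It names no marker model, baseline adjustment, dose contrast, time point or interval. Study Design does describe inference elsewhere ("Bayesian posterior probabilities are used in the randomization to adaptively assign more patients to doses with higher efficacy levels"), but those rules govern assignment and stopping, not markers.

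**The concern.** Subjects enter with acute infection and, unless hospitalized, stay on drug until symptoms have improved. Inflammatory markers would be expected to move over that period whatever the drug does. No arm is free of NAC, so a before/after summary within an arm mixes drug effect with recovery. The only internal evidence on NAC is the contrast between its three doses. Famotidine has a zero level as well.

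Descriptive statistics do not commit the analysis to those contrasts, and they make no stated use of the baseline value or of the ordered grid. Two things are at stake. A recovery-driven fall seen in every arm could be reported as a treatment effect. And with several markers and no named contrast, the one reported could be chosen after the data are seen.

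**Working it through.** The documents give no precision or power figure for any marker, so there is nothing to reproduce. The check is what the same data could deliver.

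**From the documents:** 3 NAC levels × 4 famotidine levels = 12 arms; 3 subjects per arm initially, so 36 in all; randomization within zone; zones opened one after another.

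**Assumed:** log-marker SD = 1; baseline to week-1 correlation ρ = 0.5; two-sided 95% intervals; additive, linear dose effects; zones are the diagonals of the dose grid (Figure 10 is not shown).

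**1. Half-width for 1800 versus 600 mg NAC.** The SD of change is √(2(1−ρ)) = 1.0. The residual SD after baseline adjustment is √(1−ρ²) = 0.866.

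| Comparison | Calculation | Half-width (SD) |
|---|---|---|
| Two arms of 3, own SD | 2.776 × √(2/3) × 1.0 | 2.27 |
| Two arms of 3, SD pooled over 12 arms | 2.064 × √(2/3) × 1.0 | 1.69 |
| All 12 versus all 12, change, no model | 2.074 × √(2/12) × 1.0 | 0.85 |
| Model: baseline, NAC trend, famotidine (32 df) | 2.037 × 0.408 × 0.866 | 0.72 |

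Going from 1.69 to 0.85 is pooling over famotidine. Going from 0.85 to 0.72 is almost all baseline adjustment (factor 0.866, about 13%). For ρ = 0.3 the model gives 2.037 × 0.408 × 0.954 = 0.79; for ρ = 0.7 it gives 2.037 × 0.408 × 0.714 = 0.59.

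**2. Early stopping.** If only the first three zones complete (6 arms, 18 subjects), the standard error rises to 0.730 on 14 df: 2.145 × 0.730 × 0.866 = 1.36 SD with famotidine in mg. With famotidine coded any/none it is 1.31 SD.

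**3. Calendar time.** On diagonal zones, zone number = NAC level + famotidine level. If the marker drifts by d SD per zone, each NAC step absorbs d, so 1800 versus 600 mg (two steps) is biased by 2d. A drift of 0.36 SD per zone would give a bias of 0.72 SD, as large as the half-width.

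**4. Can zone be added?**
- With famotidine as ordered levels, the identity in step 3 makes the model rank-deficient (7 of 8 columns). With famotidine as four categories it is also not estimable.
- With famotidine in mg it can be fitted, but the half-width is 2.052 × 1.847 × 0.866 = 3.28 SD, wider than two arms of three.
- With famotidine any/none it is 2.052 × 0.659 × 0.866 = 1.17 SD. This assumes 20, 40 and 80 mg act alike. If instead the effect rises evenly over the three steps to a total F, famotidine's contribution is F/3 × (zone − NAC level). The NAC term then picks up −F/3 per step, a bias of −2F/3 for 1800 versus 600 mg.

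**The case against.** The strongest reply has four parts.

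**The comparator.** A reader might infer from 2.27 against 0.72 SD that modelling gives an interval about three times narrower than the plan's. The documents do not support that. The plan names no contrast between two arms of three, and does not say its summaries are by arm. The statisticians could pool descriptively, and a 12 versus 12 table already gives 0.85 SD. This stands.

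**The prediction.** A reader might infer that the protocol predicts a fall in IL-6 in this trial. The IL-6 sentence summarizes literature on other viruses, and Hypothesis 2 says only that treatment may affect markers. This stands too; the point rests on Hypothesis 2 and III.v.

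**Recovery and time.** A reader might infer that a dose-trend model separates drug effect from recovery, or that a zone term would finish the job. Neither holds. A NAC effect of equal size at 600, 1200 and 1800 mg looks exactly like recovery, and steps 3 and 4 show that zone can be neither safely omitted nor safely added.

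**Additivity.** The background asks whether famotidine weakens NAC through gastric pH and proposes synergy. Both are interactions, and the model has no such term.

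These limits reduce what the model can claim. They do not supply the missing marker analysis, and they are further reasons not to read within-arm falls as drug effect.

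**Conclusion.** The concern holds in a limited form. The plan poses a treatment-effect question about markers, collects baseline and repeated values, and states no analysis beyond description. A pooled, baseline-adjusted dose model is a better use of the same data: about 0.72 SD for 1800 versus 600 mg, against 0.85 SD for the best simple alternative and 1.69 to 2.27 SD for single-arm contrasts. The figure rests on a completed 12-arm grid, ρ = 0.5 and additive linear effects; it is about 1.3 to 1.4 SD if escalation ends at 18 subjects.

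The result would be exploratory. It cannot exclude confounding with calendar time, cannot show a NAC effect that is flat over the tested doses, and cannot address interaction. Nor does it cover the other half of Aim 2, whether markers predict outcome. It would be wrong to say that the trial has no inferential method at all: posterior-probability rules are described for safety, efficacy and futility, just not for markers.

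**What to change.** Add to III.v, labelled exploratory:

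- **Urine markers named in Aim 2:** one linear model per marker in randomized subjects with a week-1 sample. Outcome: log week-1 value. Terms: log baseline value, NAC dose (ordered 600/1200/1800) and famotidine dose (ordered or categorical). Week 1 suits because the minimum course is 7 days unless the subject is hospitalized. Report how many lack the sample and why.
- **Glutathione and tryptase (blood only):** the same model on the end-of-treatment value, adding sample day, since that draw is timed by recovery or hospitalization. Days since enrollment are already recorded.
- **Reporting:** the NAC trend and the famotidine contrast with 95% intervals for every marker. Keep arm tables as description and state that within-arm falls are not read as drug effect.
- **Sensitivity only:** a zone-adjusted fit with famotidine any/none, with its equal-effect assumption and the resulting bias stated.
- **Limits in the text:** dose confounded with calendar time (bias 2d), no detection of a flat NAC effect, no interaction term, less precision if escalation stops early.

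Before famotidine is coded, reconcile the medication log (0 to 3 tablets of 20 mg per dose) with the 80 mg level in the Phase I Portion.

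Cost: SAP wording and a few regressions on data already collected, with no new visits or samples. The downside is the additivity assumption.

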DLT based on the trial rules and assuming the IRB and DSMB which will have also been notified of the DLT, have not imposed further restrictions, the PI will obtain from the Statistical Lead Investigator a new “Dynamic Randomization Lookup Table.” The old “Dynamic Randomization Lookup Table” will be removed from the REDCap® “File Repository” but an electronic copy will otherwise be maintained by the Lead Statistical Investigator. The new “Dynamic Randomization Lookup Table” will be uploaded into the file repository and the User Rights to the enrollment and randomization data entry forms in REDCap® will be restored.

After the investigator has determined the trial arm to which the subject has been randomized through the two-step process as described above, the investigator will verify that they correctly accessed the “Dynamic Randomization Lookup Table” in the form entitled, “COVID-19 Test Result and Drug Randomization Case Report Form.” The remainder of the form will be completed to include entry of the trial arm and verification that the correct prescription has been entered. The subject will be notified of the randomization and prescription entry. Whenever, a Randomization CRF is saved, the PI will receive an immediate electronic notification via REDCap® and the PI will then complete the Investigator Assignment Form in REDCap®, a copy of which can be found in the Appendix. It is through this form that the subject will be assigned to an individual Investigator and an individual Research Assistant for the remainder of their trial participation. The assigned Investigator and Research Assistant will be immediately notified electronically via REDCap®. The subject will be notified by the PI to which Investigator and Research Assistant they have been assigned. Unless the subject has declined a Vivify® electronic device, such device, the trial medication and paper copies of the medication log and daily diaries will be delivered to the subject’s home within 24 hours of randomization by a courier who will have the appropriate training and PPE. If the subject has declined a Vivify® electronic device, they will be required to pick-up their study drugs and paper copies of their forms at an Upstate Pharmacy.

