Subjects will be expected to take the dose combination to which they are as assigned and as prescribed. Subjects will record dates and times each medication dose was taken on their log forms which will be collected weekly. Subjects will be contact at least weekly by a Research Assistant to monitor symptoms, verify compliance with study drugs and compliance with completing medication logs and daily diary. The Research Assistant will also administer a CAP-SYM 18 during this call. The Research Assistant will communicate any concerns and all findings to a study Investigator who will later call the subject to assess how the subject is doing, discuss any concerns and will monitor the subject in the performance of a 40 Step Test for those subjects provided with an electronic device capable of measuring an Oxygen Saturation level unless the Investigator is concerned about the safety of doing so. Subjects will collect a urine sample weekly. The urine samples and the daily diary and medication log CRFs completed by the subject will be delivered by the subject or a family member within 4 hours of collection by means of the COVID-19 testing car line at Greenville Memorial Hospital. The urine specimens will be sent to Kiyatec® to measure the subject's F2-Isoprostane level, creatinine level, a cytokine panel (IL-1β, IL-2, IL-6, IL-8, IL-10, IFNγ, TNFα and GM-CSF), n-methylhistamine level and TMRSS2 levels. Subjects will self-isolate per current CDC recommendations. Subjects will remain on medication for a minimum of 7 days and unless hospitalized will continue on the medications until it has been more than 10 days beyond the start of symptoms, symptoms have improved and the subject has been without a fever for at least 24 hours without the use of a fever reducing medication. If subjects are hospitalized, then the will instructed to discontinue taking the study medications. After discontinuing study drugs for any reason, the subject will have their blood will be drawn to measure Glutathione level, a cytokine panel (IL-1β, IL-2, IL-6, IL-8, IL-10, IFNγ, TNFα and GM-CSF), and

their tryptase level; and a urine sample will be collected to measure the subject's F2-Isoprostane level, creatinine level, a cytokine panel (IL-1 β , IL-2, IL-6, IL-8, IL-10, IFN γ , TNF α and GM-CSF), n-methylhistamine level and TMRSS2 levels.

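### The Medication Log Form stops at three 20 mg famotidine tablets per dose (60 mg), but 3 of the 12 arms are assigned 80 mg, which needs four

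*Combined protocol and SAP*

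**What the plan says.** Section III) Research Design and Methods, i) Study Design, Phase I Portion, fixes the famotidine levels: "The doses to be tested for famotidine are 20 mg thrice daily, 40 mg thrice daily, 80 mg thrice daily and no famotidine". It crosses them with NAC 600, 1200 and 1800 mg thrice daily and labels the combinations 1 through 12.

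The Appendix's Medication Log Form turns the assigned dose into tablets. Its header line reads "Dose of Famotidine 20 mg tablets Assigned to Taken Thrice Daily: 0 1 2 3 (Research Staff to Circle", and the staff instruction is "Circle the assigned number of Famotidine tablets to take thrice daily". The subject is told: "You will be assigned to take one, two or three Famotidine tablets three times a day". For each dose the subject is asked only for a time: "Please enter the time of day for the correct day for each dose you take". Section III) ii) Study Procedure describes the log in the same way: "Subjects will record dates and times each medication dose was taken on their log forms which will be collected weekly".

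The same section sets the safeguards. After randomization the investigator completes a form that includes "verification that the correct prescription has been entered", the subject is told of the allocation and the prescription, and a Research Assistant makes contact at least weekly to check compliance. Subjects receive log copies at enrollment. Later, unless they declined the electronic device, the "trial medication and paper copies of the medication log and daily diaries will be delivered to" their home; those who declined it collect drug and forms from a pharmacy. Under iv) Data Collection Methods, e. Outpatient Follow-up, the Research Assistant enters the medication log into REDCap each week.

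**The concern.** The form faces the subject and is also the source of the dosing data. For the top famotidine level it does not agree with the protocol. Staff told to circle the assigned number find no option that equals 80 mg, and the highest printed option is a dose the trial does not study. A log handed over at enrollment may have nothing circled, because the arm may not yet be known. In that case the only tablet number the subject sees on it is the general sentence ending at three.

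Aim 1 is safety, and the modified 3+3 rules judge an arm on three to six subjects. If a subject in an 80 mg arm took three tablets, a dose-limiting toxicity (DLT), or its absence, would be counted at 80 mg although it arose at 60 mg. These arms include the highest combination, 80 mg with NAC 1800 mg. They also go beyond the famotidine doses in the trial cited in the Background, which went up to 160 mg/day. The assigned 240 mg/day is 1.5 times that figure (240 / 160), and the form's 180 mg/day is 1.125 times (180 / 160).

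**Working it through.** **Inputs**

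- Famotidine 0, 20, 40, 80 mg and NAC 600, 1200, 1800 mg, all thrice daily, with 12 labelled combinations (III, i, Phase I Portion).
- Three arms with NAC alone (Background, clinical rationale, item 11).
- 20 mg tablets with options 0 to 3; 600 mg capsules with options 1 to 3 (Medication Log Form).
- Minimum course of 7 days, and zero to six subjects per arm with three initially assumed (III, ii, Study Procedure).

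**1. Reproduce the number of arms.** 4 famotidine levels × 3 NAC levels = 12, as stated. The no-famotidine level gives 1 × 3 = 3 NAC-alone arms, also as stated. The 80 mg level gives 1 × 3 = 3 of 12 arms. Figure 10 is not available, but these counts do not depend on it.

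**2. Tablets needed = dose / 20 mg.**

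| Assigned dose | Tablets needed | On staff line (0–3)? | In subject instruction (1–3)? |
|---|---|---|---|
| 0 mg | 0 | yes | no |
| 20 mg | 1 | yes | yes |
| 40 mg | 2 | yes | yes |
| 80 mg | 4 | no | no |

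The option of 3 gives 3 × 20 = 60 mg, which matches no arm.

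**3. Same check for NAC.** 600 / 600 = 1, 1200 / 600 = 2 and 1800 / 600 = 3. The options 1, 2, 3 match every NAC dose. So the form is meant to encode the assigned dose, and only the famotidine entries fail. The limit of three appears in two separate places on the form, so damage from reading the PDF is an unlikely explanation.

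**4. Size if a subject in an 80 mg arm follows the form.**

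- Per day: 3 × 60 = 180 mg against 3 × 80 = 240 mg; 180 / 240 = 0.75, so 25% lower.
- Over 7 days: 7 × 180 = 1,260 mg against 7 × 240 = 1,680 mg. The shortfall is 420 mg, or 420 / 20 = 21 tablets across 7 × 3 = 21 doses.

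**5. Subjects who could be exposed.** 3 arms × 3 = 9 if all three 80 mg arms open with three subjects each. At zero to six per arm the range is 0 to 18.

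**6. What the paper log would show.** Each cell holds a time. A subject taking three tablets and a subject taking four would leave identical entries.

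**The case against.** The log is not the dosing order. Subjects are to take what was assigned and prescribed. The investigator verifies the prescription, which goes to the pharmacy, and the subject is notified. An under-dose requires either that staff circle a number that contradicts that prescription, or that the subject follows the log instead of it. Staff looking for a 4 would probably notice that it is missing, and could write it in by hand. The 80 mg level is in neither of the first two zones as described, and accrual closes between zones, so there is time to correct the form. All of this stands. It makes the harm conditional, but it does not make the form agree with the protocol.

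Four stronger readings are tempting, and the documents do not support them:

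- *That subjects in these arms will be under-dosed without anyone noticing.* Besides the prescription steps, both a Research Assistant and an investigator make contact at least weekly. With a 7-day minimum course the first required contact could fall at its end, but that is the worst case. Treatment also continues until more than 10 days after symptom onset, with improvement and no fever, and investigators may call more often.
- *That 60 mg was the intended top dose.* Nothing in the documents points to it. The Phase I section is the statement of the doses, and the form is an appendix derived from it.
- *That the lack of a tablet count is a defect in every arm.* In the other nine arms the circled number and the dose times together give the recorded dose, and changes go on the Trial Drug Adjustment form. A count is useful but optional.
- *That the dose taken could never be recovered.* That holds for the paper log alone. The REDCap Daily Medication Log and weekly assessment forms are listed but not reproduced, and may hold more.

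**Conclusion.** The form is wrong as written and should be fixed. This is an internal inconsistency between an appendix form and the protocol's dose levels, not a flaw in the escalation design. It affects the 3 of 12 arms at 80 mg. In the 3 no-famotidine arms there is a lesser fault: the subject sentence omits zero, although the staff line offers it.

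The mismatch itself needs no assumption beyond the 20 mg tablet printed on the form. The 25% lower daily dose (180 against 240 mg) assumes that a subject in an 80 mg arm follows the form rather than the prescription. How likely that is cannot be judged from the documents, because the prescription and dispensing records are not shown. The figure of 9 subjects assumes that all three arms open with three each.

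No change in any admissibility decision has been shown. The documents give no arm-specific DLT rates for 60 mg and 80 mg from which to compute one. What is at stake is that safety evidence from the top famotidine arms could be credited to a dose that was not taken, without the paper log showing it.

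**What to change.** Before any 80 mg arm opens:

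1. Change the staff line on the Medication Log Form to 0 1 2 4. Multiplied by 20 mg this gives 0, 20, 40 and 80 mg, the four protocol levels.
2. Change the subject instruction to zero, one, two or four famotidine tablets.
3. Confirm that the REDCap Daily Medication Log carries the same options.

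Optionally, add a space for tablets taken at each dose, so that a DLT can be tied to the dose received.

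The cost is one form line, one sentence and one database check, with no added subjects, visits or procedures. If anyone has already been assigned to an 80 mg arm, compare that subject's prescription, circled number and any dispensing record.
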